5. STUDY TREATMENTS

5.1. Description of Treatments

5.1.1. Study Drug

KNX100 will be provided in capsule form as either 5 mg, 25 mg, or 100 mg capsules ([Table 2](#)).

Table 2 Dose Strength Per Capsule

Study Drug	Dosage Strength/Dosage Form		Manufacturer
	KNX100 Phosphate	Free Base Equivalent	
KNX100	5 mg/capsule	3.4 mg/capsule	Quotient Sciences (formerly Arcinova Ltd).
KNX100	25 mg/capsule	16.8 mg/capsule	Quotient Sciences (formerly Arcinova Ltd)
KNX100	100 mg/capsule	67.1 mg/capsule	Quotient Sciences (formerly Arcinova Ltd)

5.1.2. Placebo

KNX100 matching placebo will be provided in capsule form. An equivalent number of capsules will be administered to subjects receiving placebo (e.g., the first dose of study drug will be one 5 mg capsule; subjects receiving placebo will also receive only one capsule).

5.2. Treatments Administered

Both KNX100 and placebo will be administered orally based on the assigned treatment group (refer to [Section 5.3](#)). For each cohort, a total of 8 subjects will be dosed (6 with KNX100 and 2 with placebo).

Part A will evaluate doses of KNX100 starting with 5 mg and increasing up to a maximum of 50 mg per day ([Table 3](#)). Doses post the 5 mg dose will be decided by the CRC upon review of all available data.

Part B will evaluate a low- (10 mg), and high-dose, based on the doses evaluated in Part A and the safety, tolerability, and PK of doses in the previous cohorts, administered for 7 consecutive days ([Table 4](#)). Part B (Cohort 3) will evaluate twice daily dosing of a single dose, selected based on the safety, tolerability, and PK of doses in the previous cohorts, administered for 7 consecutive days ([Table 4](#)).

5.3. Selection and Timing of Dose for Each Subject

Pertinent information for the SAD study is provided in [Section 5.3.2](#), along with the proposed dose escalation schedule in [Table 3](#).

Pertinent information for Part B is provided in [Section 5.3.3](#), along with the proposed dose escalation schedule in [Table 4](#).

Subjects in both Part A (SAD) and Part B (MAD) phases will be housed in the clinic from Day - 3 prior to each dose and remain in-house for 30 hours postdose (Day 2) for Part A and 8 days post initial dose for Part B (Day 8).

5.3.1. Sentinel Subject Review and Toxicity Management

Part A Cohorts 1 through 4 will initiate dosing with 2 sentinel subjects who are randomly assigned so that 1 subject receives KNX100 and the other receives placebo. Following dosing of study medication, site personnel will observe the sentinel subjects for 48 hours, at which time the investigator will review the safety and tolerability for both sentinel subjects. This will include housing of the sentinel subjects in the Phase 1 unit for 30 hours postdose and then a follow up phone call at approximately 48 hours postdose administration.

Data reviewed will include AEs, clinical laboratory results, vital signs, and ECGs, EEGs, and PK parameters for both subjects. PK will be evaluated to ensure that exposure has not exceeded the maximum clinical exposure cap defined in [Section 6.20.1](#). Upon acceptance of reviewed data by the site and CRC, dosing may continue for the remaining 6 subjects. The investigator will document the review and decision by email to Sponsor representatives.

5.3.2. Part A Dosing

Study drug will be administered once on Day 1. Part A dosing will commence with 2 sentinel subjects prior to dosing the remainder of each cohort (refer to [Section 5.3.1](#)).

Study drug will be administered in the morning together with a glass of tap water under a fasted state, i.e., after an overnight fast of at least 10 hours and no food is allowed for at least 2 hours after drug administration. Please refer to [Section 5.10.3](#) for information related to fluid and food restrictions both pre- and postdose.

[Table 3](#) provides the planned dose-escalation schedule. Of note, dose escalations will not exceed dose-doubling in principle.

Table 3 Planned Dose-Escalation Schedule (SAD Part A)

Cohort	Oral Daily Dose (mg/day) ¹		Total Number of Capsules (Number - Strength) ¹	
	KNX100	Placebo	KNX100	Placebo ²
1	5	0	1 capsule (1 × 5 mg)	1 capsule (1 × 0 mg)
2	15	0	3 capsules (3 × 5 mg)	3 capsules (3 × 0 mg)
3	25	0	25 mg: 1 capsule (1 × 25 mg)	25 mg: 1 capsule (1 × 0 mg)
4	50	0	50 mg: 2 capsules (2 × 25 mg)	50 mg: 2 capsules (2 × 0 mg)

Abbreviations: PK = pharmacokinetics.

¹ All dose levels beyond Cohort 1 may change based on emerging safety and PK data.

² An equivalent number of capsules will be administered to subjects receiving placebo.

*Additional cohorts may be added as required, based on safety profile and CRC authorization.

Dose escalation and de-escalation will follow the processes outlined in [Section 5.3.4](#).

5.3.3. Part B Dosing

In Cohorts 1 and 2, study drug will be administered once daily for 7 days at approximately the same time each day \pm 30 minutes. In Cohort 3, study drug will be administered twice daily, approximately 8 hours (\pm 30 minutes) apart for 7 days. Doses will be administered:

- Morning (e.g., at 11:00 am) at approximately the same time (\pm 30 minutes) each day
- Afternoon/ Evening (e.g., at 7:00 pm) at approximately the same time (\pm 30 minutes) each day

The first dose of study drug will be administered together with a glass of tap water under a fasted state i.e., after an overnight fast of at least 10 hours. For MAD Cohort 3, the second dose of study drug will be administered together with a glass of tap water under a fasted state i.e., after fasting for at least 2 hours prior to dose administration. For all cohorts, no food is allowed for at least 2 hours after drug administration. Please refer to [Section 5.10.3](#) for information related to fluid and food restrictions both pre- and postdose.

[Table 4](#) provides the planned dose-escalation schedule for Part B (MAD). Up to 2 dose strengths ranging from as low as 10 mg and up to the clinical exposure cap will be selected based on the tolerability and pharmacokinetics of the previous dose.

Table 4 Planned Dose-Escalation Schedule (MAD Part B)

Cohort	Oral Daily Dose (mg/day) ¹		Total Number of Capsules/Day (Number - Strength) ¹	
	KNX100	Placebo	KNX100	Placebo ²
1	10 (Low)	0	2 capsules (2 × 5 mg)	2 capsules (2 × 0 mg)
2	30 (High)	0	2 capsules (1 × 5 mg, 1 × 25 mg)	2 capsules (2 × 0 mg)
3	30 (bid) ³	0	2 capsules (1 × 5 mg, 1 × 25 mg) (am) 2 capsules (1 × 5 mg, 1 × 25 mg) (pm)	2 capsules (2 × 0 mg) (am) 2 capsules (2 × 0 mg) (pm)

Abbreviations: am = morning; bid = twice daily; MAD = multiple ascending dose; pm = afternoon/evening

¹ Dose levels will be based on data from Part A and emerging PK data.

² An equivalent number of capsules will be administered to subjects receiving placebo.

³ Dose to be administered twice daily, 8 hours apart (refer also to [Section 5.3.3](#)).

5.3.4. Dose Escalation

An evaluable subject is one that has been dosed, completed all assessments, and had their data reviewed by the CRC.

Blinded data to be reviewed by the CRC for each subject will include (as a minimum): PK (up to 30 hours postdose for Part A and 24 hours postdose for Part B), EEG, ECG, vital signs, pulse oximetry, neurological examination, and any adverse events.

The CRC may approve dose escalation following review of cohort data if:

- No drug related SAE's occurring within 48 hours of administration of KNX100 or placebo is observed in any subject in the dose group under evaluation.
- No drug related AE's of Grade 3 or greater are observed in 2 or more subjects within a dose group.
- The mean KNX100 C_{max} **OR** AUC does not exceed 84.9 ng/mL or 82.7 ng×h/mL respectively **and** the mean KNX100A C_{max} **OR** AUC does not exceed 26.5 ng/mL and 45.7 hr × ng/mL, respectively, the exposure associated with 1/10th of the NOEL of 2.75 mg/kg observed in the 14-day dog EEG study.
- No emergence or evidence of other PI-deemed and or medical monitor-deemed clinically significant abnormal vital signs, neurological and physical examination, or safety parameters postdose have been observed.

Dose increases will be permitted once review of data from all evaluable subjects has been performed.

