3. INVESTIGATIONAL PLAN

3.1. Overall Study Design and Plan

This is a Phase 1, FIH, single site, single treatment, 2-part, double blind, placebo controlled, randomized, single ascending dose (SAD)/multiple ascending dose (MAD) study designed to evaluate the safety and tolerability of KNX100 as compared to placebo. This study will enroll healthy volunteers.

The planned enrollment is approximately 64 male and female subjects. The total number of subjects will depend on the number of dose levels assessed in dose-escalation. Completed subjects will have received either KNX100 (active study drug) or placebo. Subjects who discontinue will be replaced to achieve the targeted number of evaluable subjects in each cohort.

Healthy subjects who meet all eligibility criteria will be sequentially enrolled and assigned to a single cohort in Cohorts 1-4 in Part A of the study or in Cohorts 1-3 in Part B of the study. Each cohort selected will evaluate 8 subjects; 6 subjects will be randomly assigned to receive KNX100, and 2 subjects will be randomly assigned to receive placebo. Each cohort will be enrolled sequentially, and the subsequent dose increase will be based on the Cohort Review Committee (CRC) evaluation of data known to date.

Additional cohorts may be added as required, based on safety profile and CRC authorization.

Part A (SAD) will initially dose 2 sentinel subjects (one with KNX100 and one with placebo) in Cohort 1. The center will review safety and tolerability up to and including the 48-hour timepoint for the sentinel subjects before dosing the remaining subjects in the dose cohort. The CRC will be informed and authorize the decision to continue with the remainder of the cohort dosing. Each subject will receive 1 dose, administered orally, of study drug. All subjects in each cohort will have their data, up to and including the 30 -hour postdose timepoint, evaluated for safety and tolerability by the CRC before opening the next dose cohort based on assessment of all available data. The dosing schedule may be extended if additional observations are needed at a particular cohort. In the absence of unacceptable AEs, the CRC may decide to open the next cohort before they have reviewed all data from all 8 evaluable subjects who have completed up to and including the 30-hour timepoint postdose.

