3.2. Rationale for Study Design and Control Group

Study Design: This study is a 2-part, single site, single treatment, double-blind, randomized, placebo-controlled, dose escalating study to assess the safety, tolerability, and PK of single and multiple ascending doses and twice daily dosing of KNX100 administered orally to healthy males and females. Investigators and subjects will be blinded to treatment; however, the site pharmacist will be unblinded. Members of the CRC will be blinded; however, specific members may be unblinded to enable evaluation of PK and safety data for dose escalation decisions if required.

The design of this study is typical of those used for FIH studies with a "dose leader" (sentinel) design to better manage the safety aspects of the study. A sentinel design will be implemented during Part A, (SAD), with 2 subjects being dosed on the first dosing day of each Cohort. Of these, one will receive KNX100, and one will receive placebo. Safety and tolerability will be reviewed for these 2 sentinel subjects by the site, and CRC, before dosing the remaining subjects in the dose cohort.

All data for subjects in each SAD cohort collected up to and including the 30-hour samples postdose will be evaluated for safety and tolerability before opening the next higher dose cohort. In each MAD cohort, data for subjects up to and including the 24-hour timepoint post morning dose on Day 8 will be evaluated for safety and tolerability before opening the next higher dose cohort. The dosing schedule may be extended if additional observations are needed at a particular cohort. In the absence of unacceptable AEs, the CRC may decide to open the next

cohort before having reviewed data from all of the evaluable subjects who have completed Day 7 in the SAD cohorts and Day 14 in the MAD cohorts.

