9.8.1. Blinded Data Review

For Part A (SAD), the CRC will review all safety and PK data of the Sentinel subjects, collected up to the 30-hour postdose timepoint, to enable decision to enroll the rest of cohort. The CRC will also conduct a blinded, cohort-escalation review after the final subject in a cohort has been dosed, using safety data from all subjects through at least the 30-hour-postdose visit, as well as

all available blinded PK and safety data from the current or previous cohorts. Upon acceptance of reviewed data, dosing for the 2 sentinel subjects in the next cohort may occur.

For Part B (MAD), the CRC will review all safety and PK data from each cohort collected up to and including the 24-hour post morning dose timepoint on Day 8. Additionally, the frequency and severity of the following events and findings will be used to determine the acceptability of escalation to the next cohort:

- Serious AEs
- Discontinuation of participation due to an AE
- Adverse events
- Clinically significant laboratory, EEG and ECG findings.
- Study medication sensitivities and reactions.

The safety observation period may be extended if additional safety data are required for any cohort. Based on all available data, a recommendation for dose escalation or changes to the protocol will be made in collaboration with the investigator.

Updated dispensing guidelines for each dose escalation will be provided based on all available data. Sponsor representatives will document cohort-escalation decisions in central files.

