3 STUDY DESIGN

3.1 General Description

This is a Phase 1, first-in-human (FIH), single site, single treatment, two-part, double-blind, placebo-controlled, randomized, single ascending dose (SAD)/multiple ascending dose (MAD) study. The planned enrollment is approximately 64 male and female subjects. The total number of subjects will depend on the number of dose levels assessed in dose-escalation. Completed subjects will have received either KNX100 (active study drug) or placebo. Subjects who discontinue will be replaced to achieve the targeted number of evaluable subjects in each cohort.

[figure not shown]
Healthy subjects who meet all eligibility criteria will be sequentially enrolled and assigned to a single cohort in Cohorts 1-4 in Part A (SAD) of the study or in Cohorts 1-3 in Part B of the study. Each cohort selected will evaluate 8 subjects who will be randomly assigned with a ratio of 6:2 to receive either KNX100 or placebo. Each cohort will be enrolled sequentially, and the subsequent dose increase will be based on the Cohort Review Committee (CRC) evaluation of data known to date. Additional cohorts may be added as required, based on safety profile and CRC authorization.

Part A (SAD) will initially dose two sentinel subjects (one assigned to KNX100 and one assigned to placebo) in Cohort 1. The center will review safety and tolerability up to and including the 48-hour timepoint for the sentinel subjects before dosing the remaining subjects in the dose cohort. The CRC will be informed and authorize the decision to continue with the remainder of the cohort dosing. Each subject will receive one dose, administered orally, of study drug. All subjects in each cohort will have their data, up to and including the 30-hour post-dose timepoint, evaluated for safety and tolerability by the CRC before opening the next dose cohort based on assessment of all available data. The dosing schedule may be extended if additional observations are needed at a particular cohort. In the absence of unacceptable AEs, the CRC may decide to open the next cohort before they have reviewed all data from all 8 evaluable subjects who have completed up to and including the 30-hour post-dose timepoint. Subjects will be housed in the clinic from Day -3 prior to study drug administration and will remain in-house for 30 hours post-dose (Day 2) for PK and safety assessments.

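### The closing condition for dose increases in Protocol 5.3.4 is met by definition, and the Part A early-opening sentence in Protocol 3.1 and SAP 3.1 can be read in a way that does not fit Protocol 9.8.1

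*Protocol*

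**What the plan says.** Protocol 5.3.4 opens with the definition: "An evaluable subject is one that has been dosed, completed all assessments, and had their data reviewed by the CRC". It ends with the condition: "Dose increases will be permitted once review of data from all evaluable subjects has been performed". Between the two it sets a per-subject data minimum ("Blinded data to be reviewed by the CRC for each subject will include (as a minimum): PK", followed by EEG, ECG and other safety items, with PK to 30 hours in Part A and 24 hours in Part B). It also lists four substantive criteria, introduced by "The CRC may approve dose escalation following review of cohort data if".

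Protocol 3.1 first says that the CRC evaluates all Part A subjects to 30 hours before the next cohort opens. It then adds an exception: absent unacceptable AEs, "the CRC may decide to open the next cohort before they have reviewed all data from all 8 evaluable subjects". SAP 3.1 carries the same exception: "before they have reviewed all data from all 8 evaluable subjects who have completed up to and including the 30-hour post-dose timepoint". Neither gives a minimum number of subjects.

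Protocol 3.2 has a second early-opening sentence with a later time reference: the CRC may open the next "cohort before having reviewed data from all of the evaluable subjects who have completed Day 7 in the SAD cohorts", with Day 14 for the MAD cohorts.

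Protocol 9.8.1 places the Part A escalation review after the cohort's last subject is dosed, "using safety data from all subjects through at least the 30-hour-postdose visit". SAP 3.4 says the same. Neither mentions an exception.

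**The concern.** This is a first-in-human trial with an identified seizure risk (Protocol 6.17.5). The sentence in the escalation section that looks like an all-subject requirement places no requirement on the CRC. It also leaves out a dosed subject who stopped early, who may be the most informative one.

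Alongside that, 3.1 and 9.8.1 do not give the CRC one clear answer on whether all 8 Part A subjects must be reviewed to 30 hours before the next dose level. The question matters because one subject can be decisive. Under 6.11.1 epileptiform discharges bar further escalation, and under 6.20 they suspend all dosing if seen in any subject. A rule of that kind works fully only when every subject's EEG has been read.

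**Working it through.** The plan gives no figure to reproduce here; Protocol 8.2 states that the study is descriptive and that no power calculation was made. The check is of logic and text, with one illustration.

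**1. The closing sentence of 5.3.4.** Let D be the dosed subjects, C those who completed all assessments, and R those whose data the CRC has reviewed.
- Definition: E (evaluable) = D ∩ C ∩ R.
- Closing condition: every member of E has been reviewed, that is, E ⊆ R.
- Since E is an intersection that includes R, E ⊆ R always holds. With 0, 2 or 8 of 8 reviewed, the condition is met each time.
- A subject in D but not in C, such as one withdrawn before the last required assessment, is never in E, so the sentence does not ask for that subject's data.
- The definition also clashes with 3.1, which speaks of evaluable subjects who have not yet been fully reviewed. Under 5.3.4 there can be none.

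**2. Early opening against the review rule (Part A).** The exception in 3.1 can be read in two main ways.
- It relaxes the *number of subjects* reviewed. Any number below 8 is then possible, while 9.8.1 and SAP 3.4 mean 8 of 8. These do not fit.
- It relaxes only the *type of data*, for example late PK. Section 9.8.1 can accommodate this, because it asks only for the blinded PK that is available. But 5.3.4 makes PK to 30 hours and EEG a minimum for each subject, and 6.11.1 puts EEG from both the sentinels and the rest of the cohort in the review package. There is still tension.

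**3. Illustration of the gap.** Inputs: 8 per cohort, 6 active and 2 placebo (Protocol 5.2); 2 sentinels, 1 active and 1 placebo, reviewed first (5.3.1). The other 6 are therefore 5 active and 1 placebo. Assumptions that are not in the documents: exactly one active subject has a finding that only the review brings out, each of the 6 is equally likely to be that subject, and j of the 6 non-sentinels, taken at random, have been reviewed at opening.

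P(not yet reviewed) = 5/6 × (6 − j)/6

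- j = 0 (2 of 8 reviewed): 5/6 × 6/6 = 83%
- j = 2 (4 of 8): 5/6 × 4/6 = 56%
- j = 4 (6 of 8): 5/6 × 2/6 = 28%
- j = 5 (7 of 8): 5/6 × 1/6 = 14%
- j = 6 (8 of 8, as in 9.8.1): 0%

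These are shares left unreviewed under the stated assumptions. They do not estimate clinical risk or predict conduct.

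**The case against.** A fair defence has five parts.

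- **3.1 may presuppose that all 8 have passed 30 hours.** Its full wording refers to subjects who have completed that timepoint, so perhaps only some data items are outstanding. This is possible, and it is why the conflict with 9.8.1 depends on the reading taken. It does not remove the tension with the per-subject minimum in 5.3.4.
- **Opening need not mean dosing.** Section 9.8.1 ties acceptance of the reviewed data to dosing the next sentinels, and screening and admission come before dosing. However, 3.1 itself uses opening as the step that the 30-hour review must precede, so the distinction is not drawn in the text.
- **Other protection remains.** The four criteria in 5.3.4 can each block escalation. Every planned Part A cohort starts with one active and one placebo sentinel, observed for 48 hours and accepted by the CRC before the other 6 are dosed (5.3.1). The EEG suspension in 6.20 does not depend on the word *evaluable*. All of this stands. The limit is that the criteria see only what has been reviewed: with the sentinels alone, the mean exposure criterion would rest on 1 active subject.
- **Part B is largely covered.** Section 3.1 has the CRC evaluate AE, PK and EEG data to Day 8 from all subjects in each MAD cohort and gives no early-opening exception there. This stands. The Day 7/Day 14 sentence in 3.2 probably means only that follow-up visits need not be awaited.
- **The CRC Plan may settle it.** Protocol 9.8 places CRC operations and its assessment schedule in that Plan, which was not available. It may state a minimum, but the early-opening sentence does not refer to it.

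A reader might infer that escalation has no effective control, or that the protocol authorises dosing the next cohort on 2 of 8 subjects. The documents support neither. The first ignores 9.8.1 and the 5.3.4 criteria. The second takes the exception in 3.1 apart from the preceding sentence of 3.1 and from 9.8.1.

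**Conclusion.** The point holds in a limited form. The circularity in 5.3.4 follows from the text and needs no assumption. The mismatch between 3.1 and 9.8.1 is an ambiguity that should be resolved: one reading of 3.1 departs from the all-subject review, and the milder reading strains the 5.3.4 data minimum. The gap is between 8 of 8 reviewed and an unstated smaller number, in Part A only.

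Severity is modest, because an all-subject review is already described elsewhere and several independent protections apply. The wording should still be changed: in a first-in-human escalation rule, the sections should give the CRC the same answer. The 14% to 83% range is illustrative only and should not be cited as a probability of harm.

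**What to change.** 1. In Protocol 5.3.4, delete the CRC-review clause from the definition of *evaluable* and set the cut for assessments at 30 hours postdose (SAD) or Day 8 (MAD).
2. Replace the closing sentence of 5.3.4 with: *Dose increases are permitted only after the CRC has reviewed the minimum data listed in this section (safety, EEG and PK) to that cut from all dosed subjects in the cohort, including available data from any who stopped early.* Naming EEG and PK matters, because the exposure cap and the EEG rule both bear on escalation.
3. Limit the early-opening text in Protocol 3.1, Protocol 3.2 and SAP 3.1 to not awaiting later data, namely the Day 7 (SAD) and Day 14 (MAD) follow-up, so that it agrees with Protocol 9.8.1 and SAP 3.4.
4. Check the CRC Plan against the revised wording.

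The cost is a protocol and SAP wording change and, if needed, an edit to the CRC Plan. The downside is possibly a short extra wait between cohorts, because the CRC could no longer open a cohort before every subject in the current one is reviewed to the cut. Sample size and assessments are unchanged.

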3.2.1. Starting Dose Justification

Animal doses (intraperitoneal [IP] and oral) assessed in primary pharmacology models were used to predict the human efficacious dose of oral KNX100. The efficacious doses administered to mice were converted to human dose equivalents per the *FDA Guidance for Industry: Estimating the Maximum Safe Starting Dose in Initial Clinical Trials for Therapeutics in Adult Healthy Volunteers (July 2005)*.

Extensive preclinical efficacy data for the target indication of opioid withdrawal has been obtained using IP injection in mice. However, to date, preclinical efficacy data following oral administration in an opioid withdrawal mouse model is unavailable. The data collected in efficacy studies evaluating the effects of KNX100 (IP) on naloxone induced opioid withdrawal models in C57BL/6 mice and KNX100 (PO) in nicotine withdrawal models allow for a reasonable estimation of an effective dose range in humans, assuming allometric scaling on a mg/kg basis and similar affinities of KNX100 to pharmacodynamic (PD) targets in humans and C57BL/6 mice. Based on the available animal data, a pharmacologically effective dose range (PAD) of approximately 0.89-1.78 mg/kg of KNX100 phosphate (equivalent to 53-107 mg/day in a 60 kg adult) was anticipated for reducing the symptoms of opioid withdrawal in humans.

The human PK parameter estimates for CL/F and V/F based on single dose preclinical data from mouse, rat, and dog studies following oral administration was predicted using multiple allometric scaling approaches. Overall, the range of doses using multiple methods of prediction ranged from 53 to 125 mg. However, clearance in the rodent was much lower than in human, resulting in higher exposure levels that would not be achieved at the 53 or 125 mg doses. The AUC following a 3.7 mg/kg IP dose in the mouse was 23.3 h*ng/mL. Using the observed human CL/F value of 356,000 mL/h, a dose required to achieve the target AUC can be obtained using the following equation: $\text{Dose (ng)} = \text{CL (mL/h)} \times \text{AUC (h} \times \text{ng/mL)}$. Using this formula, a total daily dose of 8.3 mg was derived. However, the C_{max} following the 3.7 mg/kg IP dose was 45.5 ng/mL. Based on the clinical data already obtained, a dose of around 20 mg could be estimated to achieve a C_{max} of 46 ng/mL.

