3.2.2. Maximum Dose

An upper limit of 35 mg per day is supported by the nonclinical data and human PK data, specifically by exposure at the 1/10th of the NOEL of 2.75 mg/kg established in the 14-day dog EEG study, however this will be guided by emerging safety and PK data. Dose escalation will stop at any time if unacceptable safety findings are identified or if the maximum concentration (C_{max}) or area under the curve (AUC) exceeds or is likely to exceed 1/10th of the exposure associated with the NOEL of 2.75 mg/kg seen in the 14-day dog EEG study (84.9 ng/mL or 82.7

h×ng/mL for KNX100 and 26.5 ng/mL and 45.7 hr × ng/mL for KNX100A, respectively). In this case, the CRC may stop the study, or modify the dose downwards in subsequent cohorts.

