6.20.1. Maximum Clinical Exposure

Clinical PK will be considered as criteria for escalation of clinical doses. Dosing will not exceed $1/10^{\text{th}}$ of the exposure associated with the NOEL of 2.75 mg/kg observed in the 14-day dog EEG study (KNX100 C_{max} and $AUC_{0-\text{last}}$ of 84.9 ng/mL and 82.7 hr \times ng/mL, respectively and KNX100A C_{max} and $AUC_{0-\text{last}}$ of 26.5 ng/mL and 45.7 hr \times ng/mL, respectively).

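### Read literally, the exposure condition in Protocol 5.3.4 can be met by a cohort whose exposure stops escalation under 3.2.2, so the two sections and 6.20.1 need one rule

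*Protocol*

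**What the plan says.** Three sections of the protocol use the same four caps: for KNX100, Cmax 84.9 ng/mL and AUC 82.7 h×ng/mL; for KNX100A, Cmax 26.5 ng/mL and AUC 45.7 h×ng/mL. All are one tenth of the exposure at the no-effect dose in the 14-day dog EEG study.

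- **5.3.4 (Dose Escalation)** is a permission list: "The CRC may approve dose escalation following review of cohort data if" a set of conditions is met. The exposure condition has two parts. The first is "The mean KNX100 C_{max} OR AUC does not exceed 84.9 ng/mL or 82.7 ng×h/mL respectively"; the second is "the mean KNX100A C_{max} OR AUC does not exceed 26.5 ng/mL and 45.7 hr × ng/mL, respectively". The word OR inside each part and the word *and* between the parts are in bold.
- **3.2.2 (Maximum Dose)** is a stop rule. Escalation ends on unacceptable safety findings, and there is a separate exposure trigger: "if the maximum concentration (C_{max}) or area under the curve (AUC) exceeds or is likely to exceed 1/10th of the exposure". The reference is the same dog dose. The CRC may then stop the study or lower the dose in later cohorts.
- **6.20.1 (Maximum Clinical Exposure)** opens with "Clinical PK will be considered as criteria for escalation of clinical doses". It then says that dosing will stay within the Cmax and AUC0-last limits, listed together.

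**The concern.** A rule to stop if either parameter is over its cap, and a rule to proceed if either parameter is within its cap, are not complements. When one cap of an analyte is breached and the other is not, the stop rule says stop and the permission rule says the condition is met.

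Section 3.2.1 makes CNS effects in animals, including convulsions, the primary basis for the dose regimens. Section 6.17.5 names monitoring of maximum plasma exposure as one of two mitigations of seizure risk. Section 5.3.2 sends Part A escalation to the process in 5.3.4. The CRC therefore has two exposure tests that can give different answers on the same PK data.

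**Working it through.** **1. The logic, with no PK assumption.** Each of the four caps is either met or breached, giving 2^4 = 16 patterns.

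- 5.3.4 read literally: for each analyte, 3 of the 4 patterns have at least one parameter within its cap, so 3 × 3 = 9 patterns pass.
- 3.2.2: only the pattern with no breach passes, so 1 passes.
- They disagree in 9 − 1 = 8 patterns. In each of these, one or two caps are breached, but never both caps of the same analyte.

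**2. The plan's own dose calculation.** Section 3.2.1 uses Dose = CL/F × AUC with observed human CL/F of 356,000 mL/h and a target AUC of 23.3 h×ng/mL. 356,000 × 23.3 = 8,294,800 ng = 8.29 mg, which reproduces the stated 8.3 mg.

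**3. Illustration for KNX100.** Inputs are that CL/F, and from 3.2.1 that "a dose of around 20 mg could be estimated to achieve a C_{max} of 46 ng/mL", or 46/20 = 2.3 ng/mL per mg. The assumptions are linear PK, CL/F on a phosphate basis, and AUC to infinity close to AUC0-last. The last is needed because 8.7 defines CL/F from AUC to infinity, whereas the cap in 6.20.1 is on AUC0-last.

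- Dose at the AUC cap: 356,000 × 82.7 = 29,441,200 ng ≈ 29.4 mg.
- Dose at the Cmax cap: 84.9 / 2.3 ≈ 36.9 mg.

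Between these doses only the AUC cap is breached.

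**4. Sensitivity to the salt basis.** Section 3.2.1 does not say whether CL/F refers to phosphate or free base. Table 2 gives 67.1 mg base per 100 mg phosphate. On a free-base basis the AUC cap is reached at 29.44 / 0.671 ≈ 43.9 mg phosphate. The gap then runs from 36.9 to 43.9 mg, with Cmax as the breached parameter.

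| Dose (mg phosphate) | Cmax = 2.3 × dose (cap 84.9) | AUC, phosphate basis = dose/CL/F (cap 82.7) | AUC, free-base basis = 0.671 × dose/CL/F (cap 82.7) |
|---|---|---|---|
| 25 | 57.5 | 70.2 | 47.1 |
| 30 | 69.0 | 84.3 | 56.5 |
| 35 | 80.5 | 98.3 | 66.0 |
| 50 | 115.0 | 140.4 | 94.2 |

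On the KNX100 part alone, the two rules agree at 25 mg (both pass) and at 50 mg (both fail) on either basis. They disagree at 35 mg on the phosphate basis only. At 30 mg the phosphate-basis AUC is 84.3/82.7 = 1.019 times the cap, an excess of about 2%. That excess vanishes if CL/F is above 30,000,000 / 82.7 ≈ 362,800 mL/h, or if a little over 2% of the excess-sized area is extrapolated beyond the last quantifiable sample.

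**The case against.** The best defence is that 5.3.4 is loose drafting and means that neither parameter may exceed its own cap. Sections 3.2.2 and 6.20.1 support that intent. The wording of the condition is also uneven: the KNX100 caps are joined by *or* and the KNX100A caps by *and*, so its connectives are weak evidence of any precise rule. This stands as a possible reading. It does not settle the matter, because the text does not state it, and setting a bold OR against a bold *and* points towards the literal reading.

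Some stronger conclusions are tempting, but the documents do not support them.

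- *That the protocol lets a cohort escalate past a cap.* Passing the exposure condition of 5.3.4 authorises nothing by itself. The list is permissive, while 3.2.2 and 6.20.1 are mandatory. Sections 3.2 (Dose), 5.3.1 and 6.12.1 all refer to the 6.20.1 limit.
- *That every dose in the gap passes 5.3.4.* The KNX100A part and the safety conditions must also be met, and the documents give no human KNX100A exposures.
- *That the planned 30 mg cohort breaches the cap.* The excess is about 2% on one set of assumptions and absent on the other. Section 3.2.2 itself says that human PK supports 35 mg per day at this limit, which sits badly with a computed AUC of 98.3. Either the simple scaling or the phosphate basis may be wrong.
- *That the cap is the only protection.* EEG is the other named mitigation. Section 6.11.1 bars further escalation if epileptiform discharges appear, and 6.20 suspends dosing pending CRC review.

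**Conclusion.** The wording conflict holds, and it rests on the text alone. Read literally, 5.3.4 and 3.2.2 give different answers in 8 of 16 patterns of the same four caps. In a first-in-human study with an animal convulsion signal, an exposure threshold for escalation should not depend on inferring what a connective was meant to say.

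The dose figures carry much less weight. They show that the gap could fall near doses the protocol contemplates: 35 mg on the phosphate basis, 30 mg only marginally, and neither on the free-base basis. They do not show that any cohort has breached or will breach a cap. A reader might also infer that the 3.2.2 rule must be the correct one. The documents show only that the sections differ, and the choice belongs to the sponsor.

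**What to change.** The sponsor should reconcile 3.2.2, 5.3.4 and 6.20.1, and the matching text of the CRC Plan, to a single exposure rule. Four items need the same answer in each place:

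- the connective between Cmax and AUC within an analyte, worded so that the permission rule and the stop rule are exact complements;
- the AUC parameter: 6.20.1 names AUC0-last, while 3.2.2 and 5.3.4 give no interval;
- the basis: 5.3.4 tests cohort means, 3.2.2 does not say, and 6.12.1 refers to exposure in individual subjects;
- whether a likely breach counts: 3.2.2 includes it and 5.3.4 does not.

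This review does not say which rule is right. The cost is a short protocol amendment and a matching line in the CRC Plan, with no new data. The downside is that the escalation decision at a given exposure may change, depending on the rule the sponsor confirms.
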